6.3. Appendix 3: Demographic and Baseline Characteristics

Participant demographic variables and baseline characteristics will be summarized by treatment group for the ITT Population, the MPP, and the Maintenance W16 Escape Population. The summary will also be created by treatment group in the ITT Population by participants who experienced or did not experience conjunctivitis adverse events defined using Customized MedDRA Query (CMQ) PTs as described in the Compound Level Safety Standards during the Induction Period. In addition, participant disease characteristics at Week 16 will be summarized by treatment group for the MPP. The continuous variables will be summarized using descriptive statistics and the categorical variables will be summarized using frequency counts and percentages. No formal statistical comparisons will be made between treatment groups unless otherwise specified.

The following demographic information will be included:

- Age
- Age group (Adolescents (12<18), Adults \geq 18)
- Age group (Adolescents (12<18), Adults \geq 18 - < 65, \geq 65 - < 75, \geq 75)
- Sex (male, female)
- Race (American Indian or Alaska Native, Asian, Black or African American, Native Hawaiian or Other Pacific Islander, White, Multiple, Other, Not Reported)
- Weight (kg)
- Weight category (< 60 kg, \geq 60 to < 100 kg, \geq 100 kg)
- Height (cm)
- Body mass index (BMI) (kg/m²)
- BMI category: Underweight (< 18.5 kg/m²), Normal (\geq 18.5 and < 25 kg/m²), Overweight (\geq 25 and < 30 kg/m²), Obese (\geq 30 and < 40 kg/m²), Extreme obese (\geq 40 kg/m²)
- Alcohol use (Never, Current, Former)
- Tobacco use (Never, Current, Former)

By-participant listings of basic demographic information for the ITT Population will be provided.

The following baseline disease/clinical characteristics will be included:

- Age at onset (years): calculated as the difference between date of onset of AD and the date of birth
- Duration since AD onset (years): calculated as the difference between date of Informed Consent and the date of onset of AD
- Duration since AD onset category (0 to < 2 years, 2 to < 5 years, 5 to < 10 years, 10 to < 20 years, \geq 20 years)

- Anatomical area affected by atopic dermatitis:
 - Head
 - Trunk (internal/medial axillae and groin)
 - Upper extremities (includes external axillae)
 - Lower extremities (includes buttocks and feet)
 - At least 2 areas
- Atopic Dermatitis treatment used in the past defined in [Appendix 13](#)
 - None
 - Topical corticosteroids
 - Topical calcineurin inhibitors
 - Crisaborole
 - Topical Janus kinase inhibitor
 - Topical phosphodiesterase 4 inhibitor
 - Systemic corticosteroids
 - Immunosuppressant
 - Biologics
 - Phototherapy
 - Photochemotherapy
- Investigator's Global Assessment for AD (IGA) score: 3 versus 4
- Eczema Area and Severity Index (EASI) score
- SCORing Atopic Dermatitis (SCORAD)
- Body Surface Area (BSA)
- Itch NRS
- Itch NRS: < 4, \geq 4
- Sleep loss due to itch
- Sleep loss due to itch < 2, \geq 2
- Skin pain NRS
- Patient-Oriented Eczema Measure (POEM)
- Dermatology Life Quality Index (DLQI)
- Children Dermatology Life Quality Index (CDLQI)

- Work Productivity and Activity Impairment – Atopic Dermatitis (WPAI-AD)
 - Employment status: Employed, Not employed
 - Absenteeism
 - Presenteeism
 - Overall work impairment
 - Activity impairment
- Hospital Anxiety Depression Scale (HADS)
 - Total score
 - Anxiety domain score
 - Depression domain score
- Asthma Control Questionnaire (ACQ-5) (among participants who report comorbid asthma)
- Thymus and activation-regulated chemokine (TARC)
- Baseline Columbia-Suicide Severity Rating Scale (C-SSRS) in lifetime: Category 1 – Wish to be Dead, Category 2 – Non-specific Active Suicidal Thoughts, Category 3 – Active Suicidal Ideation with Any Methods (Not Plan) without Intent to Act, Category 4 – Active Suicidal Ideation with Some Intent to Act, without Specific Plan, Category 5 – Active Suicidal Ideation with Specific Plan and Intent, Category 6 – Preparatory Acts or Behavior, Category 7 – Aborted Attempt, Category 8 – Interrupted Attempt, Category 9 – Actual Attempt (non-fatal), and Self-injurious behavior without suicidal intent

6.4. Appendix 4: Medical History

Medical histories are defined as the conditions/events recorded on the *Pre-Existing Conditions and Medical History Details* eCRF with a start date prior to the first study drug injection.

The number and percentage of participants with medical histories will be summarized for the overall ITT Population by treatment group and by treatment and age groups for the ITT Population using the MedDRA PT nested within SOC.

The number and percentage of participants with specific medical history events of interest pre-specified on the *Prespecified Medical History* eCRF (hand dermatitis, facial dermatitis, conjunctivitis, herpes zoster, and others) will be summarized for the overall ITT Population, the MPP, and the Maintenance W16 Escape Population by treatment group and by treatment and age groups.

6.5. Appendix 5: Treatment Compliance

Treatment compliance with investigational product will be summarized for participants who have at least one dose for the Safety Population in the Induction Period and for the MPP during the Maintenance Period. Treatment compliance for each participant will be calculated as:

$$\text{Treatment compliance (\%)} = 100 \times \frac{\text{Total number of injections administered}}{\text{Total number of injections expected}}$$

- The number of injections expected can be derived from the study drug dispense dataset.

- The total number of injections administered will be based on the response to the question “Was dose administered?” on the *Exposure as Collected* eCRF page.

The number of injections expected at each visit and total number of injections up to each visit during the Induction Period are as follows:

Visit	W0	W2	W4	W6	W8	W10	W12	W14 ^a
# injections at each visit	2	2	1	1	1	1	1	1
Total # injections up to each visit	2	4	5	6	7	8	9	10

Abbreviation: W = week.

^a Last injection during the Induction Period occurs on Week 14.

The number of injections expected at each visit and total number of injections up to each visit during the Maintenance Period are as follows:

Timepoint	W16	W18	W20	W22	W24	W26	W28	W30	W32	W34
Visit	W16	W18	W20		W24		W28		W32	
# injections at each visit	2	2	1	1	1	1	1	1	1	1
Total # injections up to each visit	2	4	5	6	7	8	9	10	11	12

Abbreviation: W = week.

Timepoint	W36	W38	W40	W42	W44	W46	W48	W50	W52	W54
Visit	W36		W40		W44		W48		W52	
# injections at each visit	1	1	1	1	1	1	1	1	1	1
Total # injections up to each visit	13	14	15	16	17	18	19	20	21	22

Abbreviation: W = week.

Timepoint	W56	W58	W60	W62	W64	W66 ^a	W68
Visit	W56		W60		W64		W68
# injections at each visit	1	1	1	1	1	1	0
Total # injections up to each visit	23	24	25	26	27	28	28

Abbreviation: W = week.

^a Last injection during the Maintenance Period occurs on Week 66.

A participant will be considered compliant if he or she received $\geq 75\%$ of the expected number of injections in the respective treatment period while enrolled in the study. Descriptive statistics for

percent compliance will be summarized. Sub-intervals of interest, such as compliance between visits, may also be presented.

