### 1.3. Schedule of Activities (SoA)

#### Study Schedule Protocol J2T-JE-KGAL

##### Induction Period: Screening Through Week 16

Visit Number	Screening	Induction Period										Comments
		1	2	3	4	5	6	7	8	9	10	
Weeks from Randomization	–	0	2	4	6	8	10	12	14	16		
Days from Randomization	–	0	14	28	42	56	70	84	98	112		
Visit Tolerance Interval (days)	-7 to -30	–	±3	±3	±3	±3	±3	±3	±3	±3	±3	
Informed consent/assent	X											
Inclusion and exclusion criteria	X	X										
Medical history	X	X										
Demography	X	X										
Review of immunization record	X											Adolescents only
IWRS entry	X	X	X	X	X	X	X	X	X	X		
Randomization			X									X
Dispense background TCS	X	X	X	X	X	X	X	X	X	X		
Weigh (tube with cap) and record returned background TCS			X	X	X	X	X	X	X	X		
Administer study intervention		X	X	X	X	X	X	X	X	X		Administered by site personnel. At Visit 10, participants or their caregiver will administer study intervention under site personnel supervision. At Visits 2 and 3: 2 injections At Visit 10 for participants in the Escape Arm: 2 injections All other visits: 1 injection

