**Study Schedule Protocol J2T-JE-KGAL****Maintenance Period: Week 18 to Week 40/Escape Arm**

	Maintenance Period							Comments
	11	12	13	14	15	16	17	
Visit Number	11	12	13	14	15	16	17	
Weeks from Randomization	18	20	24	28	32	36	40	
Days from Randomization	126	140	168	196	224	252	280	
Visit Tolerance Interval (days)	±5	±5	±5	±5	±5	±5	±5	
IWRS entry	X	X	X	X	X	X	X	
Dispense background TCS	X	X	X	X	X	X	X	
Weigh (tube with cap) and record returned background TCS	X	X	X	X	X	X	X	
Dispense IP for home treatment		X	X	X	X	X	X	
IP returned and compliance assessed			X	X	X	X	X	
Administer study intervention	X	X (every 2 weeks)					At Visit 11, participants or their caregiver will administer study intervention under site personnel supervision. Subsequent administration will be administered by participants or their caregiver at home. At Visit 11, for participants in the Escape Arm: 2 injections. All other visits: 1 injection.	
Safety								
Vital signs	X	X	X	X	X	X	X	
Physical examination including height and weight					X			
Concomitant medications/procedures	X	X	X	X	X	X	X	
Adverse events	X	X	X	X	X	X	X	
Investigator Scales								
IGA, EASI	X	X	X	X	X	X	X	
SCORAD	X	X	X	X	X	X	X	

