**Table 2. Maintenance Period Dosing Schedule by Treatment Group**

Treatment Assignment in Induction Period (Blinded)	Treatment Assignment in Maintenance Period	Weeks 16, 20, 24, 28, 32, 36, 40, 44, 48, 52, 56, 60, and 64	Weeks 18, 22, 26, 30, 34, 38, 42, 46, 50, 54, 58, 62, and 66
Lebrikizumab 250 mg Q2W	Lebrikizumab 250 mg Q2W	1 active injection	1 active injection
	Lebrikizumab 250 mg Q4W	1 active injection	1 placebo injection
Lebrikizumab 250 mg Q4W	Lebrikizumab 250 mg Q4W	1 active injection	1 placebo injection
Placebo	Placebo	1 placebo injection	1 placebo injection

Abbreviations: SC = subcutaneous; Q2W = every 2 weeks; Q4W = every 4 weeks.

Notes: Information provided in this table may change throughout the study. Injections are given SC.

### Participants Entering Escape Arm at Week 16

Participants who achieve neither an IGA 0 or 1 nor an EASI-75 response (<EASI-75) at Week 16 will move to the Escape Arm.

Participants who require high-potency topical or systemic rescue treatment for AD during the Induction Period will be eligible for treatment in the Escape Arm. Participants receiving systemic rescue medication in the Induction Period will be required to washout for 5 half-lives prior to initiating treatment in the Escape Arm.

Participants who are eligible for the Escape Arm at Week 16 will receive blinded loading doses at Week 16 and 18, based on their prior treatment assignment, followed by 250 mg lebrikizumab Q2W through Week 68 in the Escape Arm in an open-label fashion. Participants not achieving an EASI-50 response at 2 consecutive visits in the Escape Arm after Week 32 of treatment will be terminated from the study.

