**Table 3. Escape Arm Dosing Schedule by Treatment Group**

Treatment Assignment in Induction Period	Treatment Assignment in Maintenance Period	Escape Arm (Blinded: Week 16 and 18)	Escape Arm (Unblinded after Week 20)
Participants Entering Escape Arm at Week 16			
Lebrikizumab 250 mg Q2W	Escape Arm (Lebrikizumab 250 mg Q2W)	Week 16: 1 active and 1 placebo injection Week 18: 1 active and 1 placebo injection	One active injection Q2W during Weeks 20 to 66
Lebrikizumab 250 mg Q4W		Week 16: 2 active injections Week 18: 2 active injections	
Placebo	Escape Arm (Lebrikizumab 250 mg Q2W)		

Abbreviations: SC = subcutaneous; Q2W = every 2 weeks; Q4W = every 4 weeks.

Notes: Information provided in this table may change throughout the study. Injections are given SC.

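### SAP Appendix 5 expects 28 maintenance injections for the MPP; Protocol Table 2 schedules 26, and 28 is the count for entry to the Escape Arm at Week 16

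*SAP*

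**What the plan says.** SAP 6.5 defines compliance as 100 times injections administered divided by injections expected, and calls a participant compliant at 75% or more of the expected number in the treatment period. The summary is produced "for the Safety Population in the Induction Period and for the MPP during the Maintenance Period". No other maintenance population is named.

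On the denominator, the section first says "The number of injections expected can be derived from the study drug dispense dataset". It then prints explicit counts: "The number of injections expected at each visit and total number of injections up to each visit during the Maintenance Period are as follows". The maintenance table shows 2 at Week 16, 2 at Week 18, 1 at every timepoint from Week 20 to Week 66 and 0 at Week 68, with a running total that ends at 28. It adds: "Sub-intervals of interest, such as compliance between visits, may also be presented".

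The protocol schedules these injections in three places:

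- **Table 2** ("Maintenance Period Dosing Schedule by Treatment Group") gives 1 injection, active or placebo, at each listed week from 16 to 66 in every blinded maintenance group.
- **Table 3**, for participants entering the Escape Arm at Week 16, gives 2 injections at Weeks 16 and 18. For those treated Q2W in induction it reads "Week 16: 1 active and 1 placebo injection Week 18: 1 active and 1 placebo injection". One injection every 2 weeks follows from Week 20 to Week 66.
- **The Schedule of Activities** comments read "At Visit 10 for participants in the Escape Arm: 2 injections All other visits: 1 injection" for Week 16 and "At Visit 11, for participants in the Escape Arm: 2 injections. All other visits: 1 injection" for Week 18.

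Under SAP Section 3, MPP members are Week 16 responders on lebrikizumab, and their data are presented only up to entry into the Escape Arm.

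**The concern.** The expected count printed for the MPP is not the MPP's schedule. It carries two extra injections, one at Week 16 and one at Week 18, that the protocol gives only to participants who enter the Escape Arm at Week 16. With that table as denominator, no MPP participant can reach 100%, and some adherent participants fall below 75%.

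Protocol 9.4.2.4 requires noncompliant participants to be listed by treatment and leaves the details to the SAP, so an error here goes straight into that listing. The distortion is largest for those who stop early. The excess count is the same in all three MPP groups, but the false flags fall on early exit and need not be balanced across groups.

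SAP 6.7 gives receipt of less than 75% of expected injections as an example of an important deviation, and it summarizes deviations for the Maintenance Period. The error could carry over there, but that depends on the Trial Issues Management Plan, which is a separate document not available for this review.

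**Working it through.** **Inputs.** SAP 6.5 maintenance and induction tables; Protocol Tables 1, 2 and 3; the 75% threshold in SAP 6.5.

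**Step 1. Reproduce the SAP total.** Weeks 16, 18, ..., 66 are 26 timepoints. Two of them carry 2 injections and 24 carry 1: 2 + 2 + 24 = 28, as printed.

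**Step 2. Check the counting convention.** The induction table in the same appendix totals 2 + 2 + 6 = 10. Protocol Table 1 gives 2 + 2 + 3 + 3 = 10. The two agree, so a different way of counting does not explain the maintenance figure.

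**Step 3. Count the protocol schedules.**

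- Table 2 (blinded maintenance): 13 timepoints in one column and 13 in the other, 1 injection each = 26.
- Table 3 (Escape Arm from Week 16): 2 + 2 + 24 = 28.

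The SAP table matches Table 3, not Table 2.

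**Step 4. Completers, if the SAP table is the denominator.**

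| Injections received | Out of 26 | Out of 28 | Class at 75% |
|---|---|---|---|
| 26 | 100% | 92.9% | compliant both ways |
| 21 | 80.8% | 75.0% | compliant both ways |
| 20 | 76.9% | 71.4% | **changes to noncompliant** |
| 19 | 73.1% | 67.9% | noncompliant both ways |

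The threshold is 0.75 × 26 = 19.5, so 20 injections, against 0.75 × 28 = 21. Only a count of exactly 20 changes class.

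**Step 5. Fully adherent participants who stop early.** Score = Table 2 running count / SAP running count at the last dose. The correct score is 100% in every row.

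| Last dose | Received / expected | Score |
|---|---|---|
| Week 16 | 1/2 | 50.0% |
| Week 18 | 2/4 | 50.0% |
| Week 20 | 3/5 | 60.0% |
| Week 22 | 4/6 | 66.7% |
| Week 24 | 5/7 | 71.4% |
| Week 26 | 6/8 | 75.0% |
| Week 28 | 7/9 | 77.8% |
| Week 52 | 19/21 | 90.5% |
| Week 66 | 26/28 | 92.9% |

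The first five rows are classed as noncompliant. From Week 26 the score is at or above 75.0%.

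**Step 6. Fully adherent participants who escape, assuming the count stops at escape.** Counting doses before the escape visit: Week 20 gives 2/4 = 50.0% and Week 24 gives 4/6 = 66.7% (60.0% and 71.4% if the dose at the escape visit is counted). Week 28 gives 6/8 = 75.0% and Week 64 gives 24/26 = 92.3%. So 2 of the 12 escape visits produce a false noncompliant flag, and the other 10 do not.

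If counting instead continues after escape, a participant who escapes at Week 20 and completes with 1 injection every 2 weeks scores 26/28 = 92.9% and is compliant.

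**Step 7. Sub-interval.** For Weeks 16 to 18 the best possible MPP score is 2/4 = 50.0%.

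**The case against.** The strongest reply is that the harm is conditional. The only source that the section names for the expected number is the dispense dataset, and no sentence makes the table the denominator. If dispensing follows Table 2, every MPP percentage is right. This stands as a limit on the consequence. It does not rescue the table, which is still wrong for the only maintenance population the section covers. Nor does permission to derive the number from the dataset settle which source governs.

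Second, the escape figures assume that counting stops at escape. The section refers to the Maintenance Period, which SAP 4.1.2 runs to Week 68 or early termination, whereas other sections say Maintenance Blinded Period when only pre-escape data are meant. The MPP definition in SAP Section 3 supports the cut-off, but the point is not settled for compliance. The early-exit scores do not need this assumption, because SAP 6.5 counts injections while the participant is enrolled.

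Third, the effect is narrow. Among completers one count changes class, the MPP summaries are descriptive with no between-group comparisons, sub-interval summaries are optional, and no efficacy estimand uses the compliance flag. All of this is correct.

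Fourth, Protocol 4.1 says that placebo injections keep the number and frequency of injections the same for all participants. That could be read as 2 injections for everyone at Weeks 16 and 18. However, Table 2 already satisfies the statement across the blinded groups with 1 injection per timepoint, and both Schedule of Activities comments limit 2 injections at those visits to the Escape Arm. It is still worth including when the passages are reconciled.

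**Conclusion.** The concern holds. The SAP expects 28 maintenance injections for a population whose protocol schedule has 26, and the 2 + 2 start is the pattern for entry to the Escape Arm at Week 16. The counts are exact and rest on no assumption.

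The effect on results depends on the table being used as the denominator. In that case every MPP percentage is understated: 92.9% in place of 100% for a perfect completer, and 50.0% to 71.4% for fully adherent participants whose last dose falls at Weeks 16 to 24. How many participants that would be cannot be known from the documents. The false flags at escape at Week 20 or 24 rest on the further assumption that counting stops at escape.

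The damage is confined to the descriptive MPP compliance summary, its noncompliance flag and possibly the maintenance deviation summary. The induction count of 10 is right, and the per-protocol set uses Induction Period deviations only, so the Week 16 analyses are not affected. The point should be corrected, but it is not critical to the trial's conclusions.

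**What to change.** In SAP 6.5:

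1. Reconcile the MPP expected-injection table with Protocol Table 2 and the Schedule of Activities, which give 1 injection per timepoint and 26 in total, and check it against the statement in Protocol 4.1 on equal numbers of injections. This concerns the denominator only and implies no view on dosing.
2. If the 2 + 2 pattern is kept, label it as applying only to participants who enter the Escape Arm at Week 16.
3. State whether the table or the dispense dataset governs the denominator.
4. State whether MPP compliance is counted to exit or escape, or through the whole Maintenance Period.

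The top category in SAP 4.7.1, 27 or more self-injections in the MPP, can be checked at the same time, since 26 scheduled injections cannot reach it.

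The cost is one SAP table and one or two sentences, with no change to data collection or trial conduct.

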6.6. Appendix 6: Prior and Concomitant Therapy

Medications will be classified into anatomical therapeutic chemical (ATC) drug classes using the latest version of the World Health Organization (WHO) drug dictionary. Medication start and stop dates will be compared to the date of first dose of treatment in each treatment period to allow medications to be classified as concomitant for each treatment period.

Prior medications are those medications that start prior to the date of first dose and stop prior to or on the date of first dose of study intervention. *Concomitant medications* are those medications that start before, on, or after the first day of study intervention of the defined treatment period and continue into the treatment period. Concomitant medications are assigned to the treatment period in which they are actually ongoing. For example, if a participant is receiving a concomitant medication during the Induction Period but has a stop date during the Induction Period, the same medication would not be listed as a concomitant medication during the Maintenance Period unless participant has a new start date.

Prior medication will be summarized for the ITT Population. Concomitant medication during the Induction Period and the Maintenance Period will be presented separately for the ITT Population and the MPP.

Specific atopic dermatitis (AD) treatment during the Induction and the Maintenance Periods will be presented by treatment groups for the ITT Population and the MPP separately based on the information collected on *Concomitant Therapy* eCRF page. This will include: (1) topical AD treatment (including TCS, TCI and crisaborole), (2) systemic AD treatment (including oral corticosteroids, immunosuppressant, biologics and phototherapy). The TCS will be presented by potency. Definition of these drugs of interest is described in [Appendix 13](#).

6.6.1. Rescue Medication for Atopic Dermatitis (AD)

Rescue medication for AD is defined as:

- any high-potency TCS as defined in [Appendix 13](#), and the response to the question “For what indication was the medication / therapy taken?” on the Concomitant Therapy eCRF page is “Rescue Therapy”
- any systemic medication as defined in [Appendix 13](#), and the response to the question “For what indication was the medication / therapy taken?” on the Concomitant Therapy eCRF page is “Rescue Therapy”

Participants who use these rescue medications will be summarized. The summary will be provided for any rescue medication use, with high-potency TCS and systemic therapy summarized separately for the Induction Period on the ITT Population, the Maintenance Blinded Period on the MPP, and the Maintenance Escape Period on the Maintenance W16 Escape Population, respectively.

Disease flares will be assessed based on rescue therapy usage. Flare is defined as initiation or intensification of rescue therapy. A summary of percentage of participants in the ITT Population, the MPP, and the Maintenance W16 Escape Population rescued by visit will be provided for the

Induction Period, Maintenance Blinded Period, and Maintenance Escape period, respectively. Kaplan-Meier curves for time to first rescue use may be generated.

